Data was analyzed using SPSS version 28.0. Assuming a moderate effect size of 0.3, a power of 0.80, an alpha of 0.05 and 15% dropout rate, the estimated sample size was 40 participants. Data was summarized using frequency (%) for qualitative variables, mean \pm standard deviation (SD) for continuous variables, and median (minimum, maximum) when the distribution was not approximately normal. The normality of the outcome variables was examined using the Shapiro wilk test and boxplots. The frequency distribution of gender between the two study groups was compared using Fisher's exact test. Mean baseline characteristics and outcome variables by study group was examined using independent t-test. Median VAS, NDI, and JPE rotation right were compared between the intervention and control groups using Mann-Whitney U test. For each study group, changes in mean outcome variables (cervical spine AROM, anxiety, neck proprioception, VAS, NDI) over time (post versus pre) were examined using paired t-test or Wilcoxon signed rank test when the distribution is not approximately normal. Changes in outcome variables by group (intervention versus control) overtime (post 2 weeks versus pre) were assessed using 2x2 mixed factorial analysis of variance (ANOVA). If there was a significant interaction between group and time, the changes are significantly different between the two groups. There was a significant difference in mean STAI_T and lateral flexion left between the intervention and control groups at baseline, thus this was controlled for baseline differences using analysis of covariance (ANCOVA). In the intervention group, we examined changes in outcome variables over time (pre versus post 30 minutes versus post 2 weeks) using repeated measures ANOVA or Friedman's test if the data was not approximately normal. If the results were significant, Bonferroni's post hoc comparisons were conducted, or Wilcoxon signed rank test were used to determine what times were significantly different. The level of significance was set at $p \leq 0.05$.

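### No primary outcome is named, and five outcome families are each tested between groups at p ≤ 0.05 with no adjustment: about a 10% to 23% chance of a false TENS finding if TENS does nothing

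*SAP*

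**What the plan says.** The SAP is one paragraph. Its between-group analysis is "Changes in outcome variables by group (intervention versus control) overtime (post 2 weeks versus pre) were assessed using 2x2 mixed factorial analysis of variance", and its decision rule is "If there was a significant interaction between group and time, the changes are significantly different between the two groups". The outcomes are listed in the sentence on within-group tests: "changes in mean outcome variables (cervical spine AROM, anxiety, neck proprioception, VAS, NDI) over time (post versus pre". One threshold covers every test: "The level of significance was set at" p ≤ 0.05.

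The only multiplicity step is a Bonferroni correction in the three-time-point analysis of the intervention arm, where "post hoc comparisons were conducted" to find which times differ. It works within one outcome and one arm, and does not touch the between-group tests across outcomes.

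Neither document ranks the outcomes:

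- **SAP sample size:** "an alpha of 0.05 and 15% dropout rate, the estimated sample size was 40 participants", with no outcome attached.
- **Protocol 8b, objective 1:** pain, anxiety, disability and proprioception together.
- **Protocol 9:** VAS, STAI, NDI and the joint position error (JPE) test on an equal footing.
- **Protocol 11:** ANOVA and an alpha of 0.05, nothing more.

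Range of motion is an outcome only in the SAP. Protocol 13 mentions it as an expected benefit.

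Some families contain more than one variable. The SAP reports "There was a significant difference in mean STAI_T and lateral flexion left between the intervention and control groups at baseline", so trait anxiety and one direction of movement are variables in their own right. Protocol 8c describes separate state and trait items. JPE is also recorded by direction, as "Median VAS, NDI, and JPE rotation right were compared between the intervention and control groups using Mann-Whitney U test" shows.

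**The concern.** Each between-group test carries a 5% risk of a false positive. With five such tests and no designated primary, the risk that at least one is falsely positive exceeds 5%, and no rule says which result answers the question whether TENS works. Protocol 8a appeals to the need for randomized evidence on TENS effectiveness, and section 13 says the study may supply evidence of efficacy. A single significant outcome could therefore be read as that evidence, with more confidence than the plan supports.

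**Working it through.** **The plan's own figures.** The documents state no error rate for the set of outcomes, so there is none to reproduce. The one design figure is N = 40. A 2×2 interaction with Cohen's f = 0.3 and a pre-post correlation of 0.3 (both readings assumed) needs 34, and 34 / 0.85 = 40. Other assumed correlations give other totals: 29 at 0.5 and 55 at 0. The figure points to no particular outcome, and the rest of the check does not depend on how it was reached.

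**Inputs.**
- Per-test level 0.05 (SAP; protocol 11), taken as two-sided because F tests are non-directional.
- Five families (SAP), or four (protocol 8b and 9).
- Completers per arm: 40 × 0.85 / 2 = 17 (SAP total and dropout; equal allocation in protocol 7).
- Correlation r between outcomes: not given, varied from 0 to 0.9.
- Number of variables if families are split: not given; eight and twelve are assumptions.

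**Step 1: independent outcomes.** Chance of at least one p ≤ 0.05 with no true effect = 1 − 0.95^k.
- k = 4: 1 − 0.95^4 = 0.185
- k = 5: 1 − 0.95^5 = 0.226
- k = 8: 1 − 0.95^8 = 0.337
- k = 12: 1 − 0.95^12 = 0.460

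**Step 2: correlated outcomes.** In a 2×2 mixed ANOVA, the interaction F equals the square of the two-sample t on the change score. Null trials were simulated with 17 per arm and equally correlated normal change scores. The r = 0 column is the exact value from step 1.

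| Tests | r = 0 | 0.3 | 0.5 | 0.8 | 0.9 |
|---|---|---|---|---|---|
| 4 (SAP test on the protocol's outcomes) | 19% | 17% | 16% | 12% | 9% |
| 5 (SAP families) | 23% | 21% | 18% | 13% | 10% |
| 8 (assumed split) | 34% | 30% | 26% | 16% | 12% |
| 12 (assumed split) | 46% | 40% | 32% | 19% | 14% |

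Using 20 per arm changes these by less than one percentage point. Correlation lowers the chance of at least one false positive but not the expected number, which for five tests is 5 × 0.05 = 0.25 at every r.

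**Step 3: do the remedies control it?** Holm's first step over five tests is 0.05 / 5 = 0.01. With independent tests the chance of any false positive is then 1 − 0.99^5 = 0.049, and in simulation it stayed between about 2.5% and 5% across r. Testing a pre-recorded primary first at 0.05, with Holm on the rest only if it is significant, gave 4.9% to 5.2% at every r.

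**Step 4: cost in power.** Two-sided t-test, 17 per arm, 32 degrees of freedom, noncentrality d × √(17/2). At alpha 0.05, 80% power needs d = 0.99 SD. At Holm's strictest step:

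| Comparisons | Strictest step | Difference for 80% power | Power at 0.99 SD |
|---|---|---|---|
| 5 | 0.05/5 = 0.0100 | 1.24 SD | 56% |
| 8 | 0.05/8 = 0.00625 | 1.30 SD | 49% |
| 12 | 0.05/12 = 0.0042 | 1.36 SD | 44% |

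**Simplification.** Every outcome is treated as one normal change-score test. The SAP uses ANCOVA for the two variables with a baseline difference; that test is also run at an unadjusted 0.05.

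**The case against.** The strongest defence is that the SAP's rule works outcome by outcome. It never says that one significant outcome makes the trial positive. In a small study with parallel outcomes, testing each at 0.05 and reporting all of them is a recognised choice. This stands in part, and it is why an exploratory label is an adequate remedy. But neither document applies that label, and protocol 13 speaks of evidence of efficacy.

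A second defence is that the outcomes overlap: the NDI has a pain-intensity section, and both anxiety scores come from one form. This also stands. Independence is the upper end for a given number of tests, so a reader who took 23% as the single figure would overstate the point. Even four tests at r = 0.9 give about 9%, however, which is nearly twice the nominal level.

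Three stronger readings are tempting, and the documents do not support them:

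- **The Mann-Whitney sentence adds further efficacy tests.** It follows directly on the sentence about baseline characteristics and names no time point, so it may concern baseline only. It shows that JPE is recorded by direction and nothing more.
- **There are more than five families, or a known large number of tests.** The SAP lists exactly five families. Only the number of variables within them is open, and eight and twelve are illustrations.
- **The main result will be chosen to suit the data.** Protocol 8a mentions proprioception first and objective 1 mentions pain first, but neither order claims priority, and nothing shows an intention to select.

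The four-test row is also not the protocol's own error rate. The protocol has three groups and an unspecified ANOVA; the row applies the SAP's test to four outcomes. Finally, a primary outcome may be recorded in material not supplied here, and the fix allows for that.

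**Conclusion.** The point holds as a matter the SAP and the report should correct, and no more than that. Followed as written, the SAP gives about a 10% to 23% chance of at least one false-positive between-group result over five families when TENS has no effect, or two to four and a half times the nominal 5% (10/5 = 2; 23/5 = 4.6). For four outcomes the range is about 9% to 19%. If families are split into eight to twelve variables it is about 12% to 46%. These ranges rest on assumed equal correlations between 0 and 0.9, on normal change scores with 17 per arm and, for the last, on assumed counts.

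The protocol's last session is on Day 30, while the SAP's between-group comparison is at two weeks. That is a separate conflict. It must be reconciled to define the comparison, but it adds no weight here.

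**What to change.** 1. List in the SAP every variable compared between groups at the final time point, once that time point is reconciled. Holm depends on this count.
2. If a dated record from before the analysis names a primary outcome, its between-group comparison at two-sided 0.05 is the deciding test. Test the others with Holm only if it is significant, or label them exploratory.
3. If no such record exists, do not choose a primary now: the SAP is in the past tense and already reports baseline results, so the choice would be post hoc. Either apply Holm across all between-group outcome comparisons, or label all of them exploratory and state that no single p ≤ 0.05 shows that TENS works.
4. Report changes within an arm, including the three-time-point analysis of the TENS arm, descriptively with confidence intervals and not as evidence of a TENS effect.

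**Cost.** No new data are needed. The exploratory label costs only wording, plus giving up a confirmatory claim. Holm costs power, by the amounts in step 4 at its strictest step; later steps are less strict. The more variables are kept in the between-group set, the higher that cost.

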- 1) To measure the immediate and short-term effects of TENS on subclinical neck or upper quadrant pain with the VAS, anxiety with the State-Trait Anxiety Inventory for Adults™, disability with neck disability index (NDI), disability and cervical spine proprioception Noraxon 3D Inertial Motion Capture System in subjects 20-40 years of age.
- 2) To measure pain, anxiety, disability, and cervical spine proprioception in subjects with and without neck or upper quadrant pain.
- 3) To compare compliance of TENS home usage in groups with and without short message system (SMS), text message, reminders.

c. Procedures involved (Research Interventions)

There will be three groups as follows: twenty subjects with no pain in the normal group; forty subjects with chronic subclinical neck or upper quadrant pain will be randomized into two groups: twenty subjects in the control group, and twenty subjects in the intervention group. The intervention group will be further randomized into two groups: ten subjects will receive instructions for home use of TENS with daily SMS text message reminders and ten subjects will receive instructions for home use of TENS without SMS text message reminders. We will aim for an equal distribution of males and females in each group.

First session (Day 1): Before starting the procedures, participants complaining of pain that are greater than 4/10 in the VAS will be excluded from the study as this will be greater of what we consider to be subclinical pain based on literature review and if the pain has been present less than three months. In addition, if participants with pain less than 4/10 pain receiving clinical pain treatment, have taken pain medication

within six hours of first session, have acute pain or contraindications for electrical stimulation would be excluded from the study. Following completion of the signing procedures, all participants will be given brief explanations before administration of the questionnaires.

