Participants in the normal group will not receive any interventions in the lab or at home and will not receive education on the use of TENS equipment.

Participants in the control group will not receive any interventions in the lab or at home and will not receive education on the use of TENS equipment.

Participants in the intervention group with daily SMS text message reminders will be provided with a TENS unit by the investigators for home use for a total of 29 days and instructed by a licensed physical therapist for its use and safety. In addition, you will be provided with a daily log sheet to track its use while receiving SMS text message reminders for compliance. Then, the participants in this intervention group will receive a 30-minute high-frequency sensory TENS treatment in lab on the pain site in the neck and upper quadrant area. After the 30-minute high-frequency sensory TENS treatment, the participants in the intervention group will again complete the VAS, STAI, and NDI. Also, cervical spine proprioception will be measured with Noraxon myoMotionTM system instrument utilizing the JPE test.

Participants in the intervention group without daily SMS text message reminders will be provided with a TENS unit by the investigators for home use for a total of 29 days and instructed by a licensed physical therapist for its use and safety. In addition, you will be provided with a daily log sheet to track its use without receiving SMS text message reminders for compliance. Then, the participants in this intervention group will receive a 30-minute high-frequency sensory TENS treatment in lab on the pain site in the neck and upper quadrant area. After the 30-minute high-frequency sensory TENS treatment, the participants in the intervention group will again complete the VAS, STAI, and NDI. Also, cervical spine proprioception will be measured with Noraxon myoMotionTM system instrument utilizing the JPE test.

Session 2 (1st follow up) (Day 8): Participants will return on day eight. Participants in the normal group will be asked to complete again complete the VAS, STAI, and NDI. Also, cervical spine proprioception will be measured with Noraxon myoMotionTM system instrument utilizing the JPE test. Participants will not receive any interventions in the lab.

Participants in the control group will be asked to complete again complete the VAS, STAI, and NDI. Also, cervical spine proprioception will be measured with

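### The SAP tests change at two weeks, but the protocol assesses outcomes only on Day 1, Day 8 and Day 30

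*SAP*

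**What the plan says.** Protocol, section 8.c, sets three sessions. The first is introduced as "First session (Day 1): Before starting the procedures" and supplies the baseline. On the same day only the intervention group is measured a second time: "After the 30-minute high-frequency sensory TENS treatment, the participants in the intervention group will again complete the VAS, STAI, and NDI", with joint position error repeated as well. Session 2 is on Day 8 and the last session is on Day 30; all groups repeat the full set of outcomes at both. The TENS unit is issued for "home use for a total of 29 days" and is returned with the daily log at the last session. Section 9 confirms three assessment visits, the third at the end of the thirty-day period.

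The SAP, a single paragraph, names one follow-up. Change by group is examined "overtime (post 2 weeks versus pre) were assessed using 2x2 mixed factorial analysis of variance (ANOVA"). Change within the intervention group is examined across "pre versus post 30 minutes versus post 2 weeks". Two further analyses name no day. The within-group tests look at change "over time (post versus pre) were examined using paired t-test" or its rank-based alternative. For two variables that differed at baseline, the SAP says "thus this was controlled for baseline differences using analysis of covariance (ANCOVA"). Day 8 and Day 30 do not appear in the SAP.

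The rest of the protocol does not settle the matter. Objective 1 is "To measure the immediate and short-term effects of TENS on subclinical neck or upper quadrant pain", with no day attached, and section 11 names ANOVA without a visit.

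**The concern.** The 2x2 mixed ANOVA is the SAP's test of whether change differs between the two randomised groups. Its follow-up level has to be a visit at which data were collected, and the protocol has no such visit at two weeks.

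Two things are at stake. The first is interpretation: an effect after one week of home use, after two weeks and at the end of the planned period are different claims. The second is completeness. If outcomes were collected on both Day 8 and Day 30, a test with one follow-up leaves one of them out, and the reader cannot judge whether the choice was made before or after the data were seen. If a single two-week visit replaced the planned schedule, both the outcome time point and the home-use period changed without a record of it.

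**Working it through.** **Inputs.** From protocol section 8.c: sessions on Day 1, Day 8 and Day 30; 29 days of home TENS; 40 participants randomised to intervention or control. From the SAP: one follow-up at two weeks, used in the 2x2 ANOVA and in the intervention-only repeated-measures ANOVA.

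**Reproducing the protocol's own figure.** Calendar days with the device before a session on Day *d* are *d* − 1. For the last session, 30 − 1 = 29, which agrees with the stated home-use period, so this way of counting matches the protocol.

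**Is any interval between visits two weeks?** 8 − 1 = 7; 30 − 8 = 22; 30 − 1 = 29. None is 14. The protocol's follow-up contact text speaks of a seven-day and a twenty-one-day period, and neither of those is 14 either.

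**Does two weeks from any session land on a visit?** 1 + 14 = Day 15; 8 + 14 = Day 22; 30 + 14 = Day 44. None is a visit. Day 15 is 15 − 8 = 7 days after Session 2 and 30 − 15 = 15 days before the last session. Taking two weeks as Day 14 instead gives gaps of 14 − 8 = 6 and 30 − 14 = 16 days, so rounding does not explain the mismatch.

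**Do the SAP's other time labels fit?** Yes. The pre-treatment and 30-minute levels correspond to the two Day 1 measurements in the intervention group. The mismatch is confined to the follow-up.

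**Time with the device at the analysed follow-up, by explanation:**

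| What the two-week label really is | Calendar days with device | Share of 29 |
|---|---|---|
| The Day 8 visit | 8 − 1 = 7 | 7/29 = 24% |
| A visit held at two weeks | 15 − 1 = 14 | 14/29 = 48% |
| The Day 30 visit | 30 − 1 = 29 | 29/29 = 100% |

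The span is 29/7 = 4.1-fold. These are calendar days, not TENS dose: the protocol gives no daily number or length of home sessions.

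**What each scenario leaves out.** If one two-week visit replaced the schedule, follow-up ended 29 − 14 = 15 days early, or 15/29 = 52% of the planned period, and no visit that was held went unused. If both protocol visits were held, the randomised groups had 40 × 2 = 80 planned follow-up assessments before dropout, and a test with one follow-up uses at most 40 of them.

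**The case against.** The strongest reply is that the SAP describes what was done. It is in the past tense, reports a baseline result, is consistent in its single follow-up, and differs from the protocol in other ways. It gives a sample size of 40 where the protocol has 60, compares two groups where the protocol has three, and analyses active range of motion, which is not in the section 9 list of assessments. On that reading a two-week visit was simply held. The tests are then valid for the data collected, two weeks can count as short-term under objective 1, and what remains is an unreported departure rather than a faulty analysis.

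Much of this is fair. A changed schedule is at least as plausible as a mislabelled visit, although 40 participants in two groups also fits the randomised part of the original design. Nothing in the SAP points directly to Day 8 or Day 30 as the true day, so the 4.1-fold span measures the reader's uncertainty, not an effect on a result. No effect on error rates is shown or claimed. Only two analyses name the two-week point; that the ANCOVA and the paired tests share it is an inference from their place in the text.

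It is also fair that contrasts at two visits add multiplicity, for which the SAP states no adjustment between groups, and that a main visit named now would be named after the results are known.

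None of this removes the contradiction. If the schedule did change, the change to the outcome time point and home-use period still has to be stated, and neither document as supplied records one.

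**Conclusion.** The point holds and must be fixed. The follow-up used in the SAP's randomised comparison of change, and in its intervention-only repeated-measures analysis, matches no protocol visit, and neither protocol follow-up has a named analysis. Depending on the explanation, the result describes 7, 14 or 29 calendar days with the device. The mismatch itself rests only on the stated days and needs no assumption. Which explanation is right cannot be settled from the documents, and the figures for shortened follow-up and unused assessments each apply under one scenario only. The extension to the ANCOVA and the paired tests is likely but not certain.

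**What to change.** Reconcile the two documents against the actual visit dates, and use the returned daily logs to confirm the home-use period in the intervention group. Then state the real visit day for the 2x2 ANOVA, the ANCOVA, the paired or signed-rank tests and the repeated-measures analysis.

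- **If Day 8 and Day 30 were both held:** replace the two-week label with those visits and report the between-group contrast at each, for example from one baseline-adjusted repeated-measures model per outcome. Declare which visit is the main one and when that was decided. If it was decided after the results were seen, say so and treat the choice as post hoc.
- **If a single two-week visit was held:** keep the 2x2 ANOVA or ANCOVA, report the changed schedule and home-use period as a departure from the protocol, and limit the conclusion to two-week effects.

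The cost is a check of dates and logs and some SAP wording, with no new data. The first case also needs the contrasts re-run in SPSS; the second needs no re-analysis.

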6. SUBJECT RECRUITMENT & SCREENING

This study will have a sample size of 60 adults (males and females) between 20 to 40 years of age. This sample size will provide us with enough power to detect the needed effect size. The estimated attrition rate is 15 percent. The participants will be recruited from the student population at Loma Linda University via flyers, posters, hand-outs, mass emails, and word of mouth. The phone script will be used when potential subjects contact us after seeing the flyer.

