9. DATA COLLECTION

The study will be conducted in the Neuroscience Research Laboratory in the SAHP-[name]. Informed consent will be obtained prior to

the beginning of the study by the graduate student investigator and other IRB approved researchers. Participants will be recruited if they are adults (males and females) aged 20-40 years old with no pain for the normal group and with neck or upper quadrant pain no greater than 4/10 in the VAS for longer than three months, not receiving clinical pain treatment, have not taken pain medication within six hours of first session, have acute pain or contraindications for TENS.

Study participants will be assessed on visits one, two and three (visit three will be at the end of the thirty-day period).

During participant's visit one, two and three the following clinical assessments will be provided:

- The VAS for pain, a subjective measure of pain intensity
- The STAI-form Y is a definitive clinical measure of state and trait anxiety in adults.
- The NDI questionnaire that measures neck disability.
- JPE test which will measure cervical spine proprioception through the Noraxon myoMotionTM system instrument.

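### The 2x2 ANOVA uses only participants with both analysed values and ignores the other scheduled follow-up; with about 6 of 40 expected to leave, a mixed model on all visits guards better against dropout bias

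*SAP*

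**What the plan says.** The SAP's between-group comparison concerns "Changes in outcome variables by group (intervention versus control) overtime (post 2 weeks versus pre"; these changes "were assessed using 2x2 mixed factorial analysis of variance (ANOVA". That is one pre value and one post value per participant. ANCOVA is used only for the two variables that differed at baseline (trait anxiety and left lateral flexion).

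The protocol collects more than this: "Study participants will be assessed on visits one, two and three" (section 9, Data Collection), which section 8c places at Day 1, Day 8 and Day 30. Section 6 adds: "The estimated attrition rate is 15 percent". The SAP builds that figure into its sample size: "15% dropout rate, the estimated sample size was 40 participants".

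Section 8c gives the control arm no lab or home intervention and no TENS education, and describes no sham. Section 11 of the protocol says only that ANOVA will be used. Neither document names an analysis set, a missing-data method or an assumption about why data are missing.

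**The concern.** A 2x2 mixed ANOVA tests the difference between arms in mean change. A participant without the post value has no change score and drops out of the test, even if seen at another follow-up. With 20 per arm and 15% attrition, about 0.15 × 40 = 6 participants are at risk of this.

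The loss need not be alike in the two arms. One arm has a daily home treatment that participants can feel working or failing; the other has nothing. If those who respond poorly early on leave the TENS arm, the remaining participants look better than the arm that was randomised, and benefit is exaggerated. The protocol's Day 8 data could correct part of this, but the planned model does not use them.

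**Working it through.** **1. Is the loss already budgeted?** Inputs from the SAP: "Assuming a moderate effect size of 0.3", "a power of 0.80", and "an alpha of 0.05 and 15% dropout rate". The effect-size metric and the pre-post correlation ρ are not given; I take Cohen's f and vary ρ. For the group-by-time interaction with m = 2 measures, the noncentrality is λ = N f² m / (1 − ρ), with 1 and N − 2 degrees of freedom.

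- ρ = 0.28 to 0.30 requires N = 34, and 34 / 0.85 = 40. This reproduces the SAP's figure.
- ρ = 0.5 requires 24, and 24 / 0.85 = 28.2, so 29. No match.
- ρ = 0 requires 46, and 46 / 0.85 = 54.1, so 55. No match.

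Losing 15% of 40 leaves 34. At ρ = 0.3, λ = 34 × 0.09 × 2 / 0.70 = 8.74 and power is 82%. At the correlation that reproduces the SAP's 40, the completers alone therefore give the planned power.

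**2. How large could the bias be?** The documents give no correlations and no dropout mechanism, so all that follows is assumed. Values are in SD units. Let r₀₈, r₀₃₀ and r₈₃₀ be the correlations among Day 1, Day 8 and Day 30, with r₈₃₀ = 0.6. Suppose that the worst 15% of one arm on some early measure leave. In large samples, the mean of that measure among those who stay shifts by φ(1.036) / 0.85 = 0.2332 / 0.85 = 0.274 of its SD.

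*Dropout by Day 8 level.* The Day 30 mean shifts by 0.274 × 0.6 = 0.16. The baseline mean of those who stay shifts too, by 0.274 × r₀₈. The ANOVA tests change, so its bias is 0.274 × (0.6 − r₀₈).

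*Dropout by Day 8 change from baseline.* The bias is 0.274 × (1 + r₈₃₀ − r₀₃₀ − r₀₈) / √(2(1 − r₀₈)).

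| r₀₈ = r₀₃₀ | By Day 8 level | By Day 8 change |
|---|---|---|
| 0.3 | 0.08 | 0.274 × 1.0 / 1.183 = 0.23 |
| 0.4 | 0.05 | 0.274 × 0.8 / 1.095 = 0.20 |
| 0.5 | 0.03 | 0.274 × 0.6 / 1.000 = 0.16 |
| 0.7 | −0.03 | 0.274 × 0.2 / 0.775 = 0.07 |

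Simulation with 20 per arm and the three worst leaving one arm gives 0.17–0.21 for dropout by change and 0.03–0.08 for dropout by level, in line with the rows for 0.3 to 0.5. For scale, the standard error of the completer contrast is about 0.41 at ρ = 0.3 and 0.345 at ρ = 0.5, so the larger bias is about half a standard error (0.21 / 0.41 = 0.51; 0.17 / 0.345 = 0.49).

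**3. What does the alternative achieve?** Given baseline and Day 8, leavers and stayers have the same Day 30 distribution under both mechanisms. A likelihood model on all three visits uses this; its simulated bias is under 0.01 for dropout by change and essentially nil for dropout by level. When dropout is random, its standard error is only about 1–4% smaller.

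**4. Where does it fail?** If dropout depends on the unseen outcome, in opposite directions by arm, a model with one post value gives these biases at ρ = 0.3 / 0.5 / 0.7: completer ANOVA −0.20 / −0.14 / −0.08; mixed model −0.25 / −0.21 / −0.14. The mixed model does not help there and is somewhat worse.

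**The case against.** The strongest reply is that the plan has already paid for this loss and that the alternative is no cure. Much of that stands.

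- A reader might infer that falling from 40 to 34 leaves the trial underpowered. The SAP does not support this: 40 is the figure after allowing for 15% dropout.
- A reader might take the 0.16 SD shift in the Day 30 mean as the bias of the planned test. It is not: under dropout by Day 8 level, the baseline shift cancels most or all of it in the change score.
- A reader might infer that anyone missing any visit is lost. Only the two analysed time points matter, and the exclusion follows from how the method works; neither document states it.
- A reader might infer that a mixed model removes dropout bias outright. It does so only when dropout depends on observed data, and in an open trial with an untreated arm that cannot be taken for granted.
- ANCOVA, which the SAP already uses for two variables, handles dropout related to baseline equally well. It does not handle dropout related to Day 8, because Day 8 is not in the model: when the three worst by Day 8 change leave, its bias is 0.10–0.12 SD.
- The SAP's two-week value matches neither Day 8 nor Day 30. If only one follow-up was in fact collected, there is no intermediate visit to recover.

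The core remains: on the protocol's own schedule, the planned test sets aside data that would protect it against a plausible form of dropout.

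**Conclusion.** The concern holds as a matter of possible bias. With about 15% dropout from one arm, the difference in change is biased by about 0.17–0.21 SD if dropout follows poor early change and by about 0.03–0.08 SD if it follows the Day 8 level. These ranges rest on assumed baseline-to-follow-up correlations of roughly 0.3 to 0.5, a Day 8 to Day 30 correlation near 0.6, and selective loss in one arm; higher baseline correlations give smaller figures. With random dropout neither method is biased and the precision gain is minor. The documents do not show that selective dropout will happen; they show that the planned test has no protection if it does. This merits a change to the SAP and does not by itself invalidate the trial.

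**What to change.** 1. Reconcile the SAP's two-week time point with the protocol's Day 8 and Day 30, so that the visits in the model are defined.
2. Replace the 2x2 ANOVA with a linear mixed model (SPSS MIXED) for each outcome: all randomised participants in their assigned arm; baseline and all scheduled follow-up visits; group, visit and group-by-visit; unstructured covariance; a small-sample degrees-of-freedom correction. The contrast is the group difference in change at the last visit.
3. State the missing-at-random assumption and add a not-at-random sensitivity analysis, for example shifting the assumed outcomes of dropouts by arm until the conclusion changes.
4. If only one follow-up was collected, say so. The gain is then limited to dropout related to baseline and about 1–3% in precision.

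The SAP is written in the past tense and reports an observed baseline difference, so the change should be dated and its timing relative to the data stated. The cost is new SAP wording and slightly more analysis work on the same data, with no change to sample size, visits or treatment.
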